Buprenorphine Stabilization and Induction onto Vivitrol for Heroin-dependent Individuals

Statistical Analysis Plan

August 17, 2017

Primary objective

Individuals dependent on heroin have low rates of successful transition onto the Vivitrol on an outpatient basis. We propose to evaluate novel procedure to initiate treatment with Vivitrol in this difficult to treat population. Participants will be stabilized on buprenorphine for three weeks followed by a rapid induction onto Vivitrol using escalating doses of oral naltrexone.

Primary Endpoint

The primary outcome measure will be the proportion of patients successfully retained to receive the first naltrexone injection (dichotomous).

Secondary Objective

It is not known which factors predict, mediate, and moderate treatment response. Therefore, we propose to collect additional measures that may reflect the physiological changes associated with opioid withdrawal and naltrexone induction as well as response to medications. We will also evaluate the impact of concurrent substance use on treatment outcome and finally evaluate the safety of proposed protocol

Secondary Endpoint

Secondary Outcomes: 1) The proportion of patients successfully retained to receive second and third Vivitrol injection (dichotomous); 2) Measures of opiate withdrawal and sleep (continuous, longitudinal); 3) Measures of mood and anxiety (continuous, longitudinal); 4) Adverse events and serious adverse events; 5) A summary measure (combining urine and self-report) reflecting urine-confirmed abstinence from opioids and urine-confirmed abstinence from other drugs.

Exploratory Objectives

We will explore which patients are most likely to benefit from this procedure. We will evaluate the feasibility and acceptability of the protocol. We will evaluate whether proposed doses of adjunctive medications are adequate.

Hypothesis

We hypothesize that a short-term treatment with buprenorphine prior to initiating treatment with naltrexone will increase the proportion of heroin-dependent patients successfully inducted onto Vivitrol. We hypothesize that at least 65% of patients will be successfully retained to receive the first naltrexone injection. Based on our experience with various induction methods a response rate of less than 45% is too low to warrant further study of this treatment approach.

Analysis Plan

Given this is a single arm efficacy trial, most of the outcomes will be expressed as descriptive statistics. The primary aim is to determine if there is sufficient efficacy for the proposed procedure to warrant future studies.

Sample Size Justification

We believe that 30 participants will allow sufficient number to observe safety and tolerability and to develop precise parameters for the protocol.

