We have been piloting an alternative method of Vivitrol induction for participants who were not successful with a 5 to 7 days method. Many of those individuals are regular users of heroin and we have observed that the main reason for treatment failure in this population was the ongoing use of heroin during the week of oral naltrexone induction. Based on our observation of more than 200 individuals that we treated on outpatient basis over the past several years we believe that there are two distinct phenomena that contribute to the maintenance of heroin use in these individuals: 1) use of heroin for its euphoric effects (positive reinforcement) and 2) use of heroin to avoid withdrawal (negative reinforcement). We hypothesize that many heroin users are unable to cope with removal of both sources of reinforcement during an abrupt stopping of heroin. Therefore, we propose a treatment approach that would separate those two sources of reinforcement, in the first stage treatment will target positive reinforcing effects of heroin and in the second stage it will target adverse effects of opioid withdrawal (negative reinforcing effects). The proposed approach involves a three-week period of stabilization on buprenorphine followed by a week-long period of opioid withdrawal concurrent with rapid escalation of oral naltrexone doses.

Specific Aims and Hypotheses

Specific Aims and Hypotheses

We hypothesize that a short-term treatment with buprenorphine prior to initiating treatment with naltrexone will increase the proportion of heroin-dependent patients successfully inducted onto Vivitrol.

Description of Subject Population

Sample #1

Specify subject population

Adults using heroin who meet criteria for opioid use disorder

Number of completers required to accomplish study aims

30

Projected number of subjects who will be enrolled to obtain required number of completers

45

Age range of subject population

18-60

Gender, Racial and Ethnic Breakdown

Both males and females will be recruited. All eligible subjects are accepted; however, past experience with recruitment for other studies in this population suggests that the sample will be 75% male, 60% Caucasian, 30% Hispanic or Latino, and 10% Black or African-American.

Description of subject population

Adult heroin users who currently meet DSM-5 criteria for opioid use disorder.

Recruitment Procedures

Describe settings where recruitment will occur

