All potential participants will be evaluated at the Substance Use and Research Center (SURC) at the New York Psychiatric Institute.

How and by whom will subjects be approached and/or recruited?

All patients will be seen by one of our psychiatrists or psychologists for a screening evaluation and mental status examination as part of routine admission procedures. Patients who are opioid dependent and appear to meet criteria are told about the study and offered further evaluation. Final informed consent for the study will be obtained after full psychiatric and medical workup is complete. Procedures for training staff physicians in each protocol and consent form include initial presentations by the Principal Investigator at weekly staff meetings, and weekly discussion of inclusion/exclusion criteria and study eligibility for each screening participant.

How will the study be advertised/publicized?

Once approved by the IRB, advertisements for the study will be placed in local newspapers and radio stations. Additionally, prospective participants are recruited by word of mouth through liaison to other local clinical services.

Do you have ads/recruitment material requiring review at this time?

No

Does this study involve a clinical trial?

Yes

YOU MUST REGISTER AT ClinicalTrials.gov IMMEDIATELY UPON RECEIPT OF IRB APPROVAL AND **PRIOR TO ENROLLMENT** OF THE FIRST SUBJECT. YOU WILL BE PROVIDED WITH A NCT REGISTRATION NUMBER ON REGISTRATION. PLEASE REVISE THIS SECTION OF THE PROTOCOL SUMMARY FORM TO INCLUDE THE NCT NUMBER AND RE-SUBMIT AS AN AMENDMENT TO THE IRB.

Concurrent Research Studies

Will subjects in this study participate in or be recruited from other studies?

No

Inclusion/Exclusion Criteria

Name the subject group/sub sample

Adult heroin users who meet criteria for current opioid use disorder

Create or insert table to describe the inclusion criteria and methods to ascertain them

1. Individuals between the ages of 18-60 (clinical interview)

2. Meets DSM-5 criteria of current opioid use disorder with six consecutive months of reported heroin use, supported by a positive urine for opiates indicating regular use of heroin

3. Seeking treatment for opioid use disorder with Vivitrol (Clinical interview)
4. Capable of giving informed consent and complying with study procedures (clinical interview)

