- 10) Painful medical condition that requires ongoing opioid analgesia or anticipated surgery necessitating opioid medications (Clinical interview psychiatrist)

- 11) Fentanyl only use, supported by a urine toxicology that is positive for fentanyl only and negative for all other opioids. (Clinical interview, urine toxicology)
- 12) Court mandated to treatment (clinical interview)

Waiver of Consent/Authorization

Indicate if you are requesting any of the following consent waivers

Waiver of consent for use of records that include protected health information (a HIPAA waiver of Authorization)

No

Waiver or alteration of consent

No

Waiver of documentation of consent

No

Waiver of parental consent

No

Consent Procedures

Is eligibility screening for this study conducted under a different IRB protocol?

No

Describe procedures used to obtain consent during the screening process

Potential participants will sign the **screening consent page of the study consent** form prior to initiating the screening process. Following review of screening informed consent, an evaluation team consisting of a Masters level research psychologist and psychiatrist meets with potential participants. The baseline evaluation includes a full battery of self-report measures, a structured psychiatric evaluation (MINI interview), Hamilton depression scale, a physical examination, and laboratory assessments. Medical screening and laboratory work, include vital signs, a physical examination, ECG, serum chemistry, liver function tests, complete blood count, and urinalysis obtained by study personnel. Pregnancy tests will be conducted for women.

Describe Study Consent Procedures

After the screening evaluation, the study physician will review the study inclusion/exclusion criteria to determine if the participant is eligible for the study based on the screening materials. If the participant is eligible for the study, they will be given the consent form to read, and review with the consenting physician. The study consent will only be signed after all of the participant's questions are asked, and after all the risks and benefits are explained to and understood by the participant. Study related procedures will only be initiated after the consent form is signed by both the participant and consenting physician.

Indicate which of the following are employed as a part of screening or main study consent procedures

Consent Form

Persons designated to discuss and document consent

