Create a table or give a brief description of the instruments that will be used for assessment

MINI- International Neuropsychiatric Interview (MINI) (30 minutes) (Screening Visit)

Psychiatric Interview (30 minutes) (Screening visit)

Medical History (Screening visit)

Physical Exam (Screening and End of Study Visits)

Urine sample for toxicology (5 min) (Daily during induction phase; bi-weekly during stabilization and post induction)

Clinical Global Impression Scale- Observer (CGI-O) (5 min) (Weekly)

Hamilton Depression Scale (HAM-D) (5 min) (Weekly)

Clinical Opiate Withdrawal Scale (COWS) (2 minutes) (Daily during induction phase; bi-weekly during stabilization and post induction)

Subjective Opioid Withdrawal Scale (SOWS)(2 minutes)(Daily during induction phase; bi-weekly during stabilization and post induction)

Systematic Assessment for Treatment Emergent Effects (SAFTEE) (3 min) (Weekly)

Concomitant Medications Form (3 min) (Weekly)

Locator Form (5 minutes) (Baseline)

Craving Scale (2 min) (Daily during induction phase; bi-weekly stabilization and post induction)

Vital Signs Nursing Form (3 min) (Daily during induction phase; bi-weekly during stabilization and post induction)

End Study Form (5 min)(End of Study)

Please attach copies, unless standard instruments are used

Off label and investigational use of drugs/devices

Choose from the following that will be applicable to your study

Research Related Delay to Treatment

Will research procedures result in a delay to treatment?

Yes

Maximum duration of delay to any treatment

A delay of up to 2 weeks is possible prior to enrollment.

Maximum duration of delay to standard care or treatment of known efficacy

Up to two weeks.

Treatment to be provided at the end of the study

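### Does the unreconciled pair of 30 participants and 45 enrolled leave the primary endpoint without a usable denominator?

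*SAP*

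**What the plan says.** The SAP, under Primary Endpoint, states: "The primary outcome measure will be the proportion of patients successfully retained to receive the first naltrexone injection (dichotomous"). Under Hypothesis it adds: "We hypothesize that at least 65% of patients will be successfully retained to receive the first naltrexone injection". It also calls a rate below 45% too low to justify further study. Under Sample Size Justification its only figure is this: "We believe that 30 participants will allow sufficient number to observe safety and tolerability and to develop precise parameters for the protocol". The Analysis Plan makes most outcomes descriptive. The SAP does not mention 45, does not use the word completer and names no analysis set.

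The protocol, under Description of Subject Population, has two form entries. Against "Number of completers required to accomplish study aims" it enters 30. Against "Projected number of subjects who will be enrolled to obtain required number of completers" it enters 45. It does not define a completer.

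Three other places in the protocol bear on what enrolment means:
- Recruitment Procedures: "Final informed consent for the study will be obtained after full psychiatric and medical workup is complete".
- Consent Procedures: "Study related procedures will only be initiated after the consent form is signed by both the participant and consenting physician".
- Research Related Delay to Treatment: "A delay of up to 2 weeks is possible prior to enrollment".

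**The concern.** A proportion needs a denominator, and the two documents attach the number 30 to two different nouns, participants and completers. If the SAP's 30 were total enrolment, the protocol's own ratio would yield only 20 completers, short of the 30 it says the aims require. If the 30 are completers, the SAP gives no N for its own primary endpoint.

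The design also loses patients before the endpoint. Study Procedures requires an opioid-negative urine late in the taper, lets only those who complete the taper go on to washout, and allows for failed naltrexone induction. An analyst could therefore choose among patients who consented, started buprenorphine, completed the taper or began naltrexone. Because the SAP sets 65% and 45% as benchmarks, the choice of N could change how the same number of injections is read.

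**Working it through.** **Inputs.** From the SAP: 30 participants, 65% hypothesised, 45% floor. From the protocol: 30 completers, 45 projected enrolled. Neither document gives an alpha, a power, a dropout rate or a pass/fail count.

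**1. Do the protocol's two figures fit together?** They imply a loss of 1 − 30/45 = 1/3, and 30 / (1 − 1/3) = 45. The pair is coherent, although the one-third is implied and not stated.

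**2. Do they fit the SAP's hypothesis?** If a completer is a patient who received the first injection, 30/45 = 66.7%, next to the hypothesised 65%. Working back, 30/0.65 = 46.2 enrolled, close to 45. Expected injections from 45 enrolled are 45 × 0.65 = 29.25 at the hypothesis and 45 × 0.45 = 20.25 at the floor. The exact binomial chance of at least 30 injections from 45 is 0.475 at 65% and 0.0028 at 45%. On this reading 30 is roughly the expected number of successes and 45 is the cohort.

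**3. Could 30 be total enrolment?** Then 30 × (30/45) = 20 completers, against the 30 required. This reading must set aside the protocol's explicit 45, and no other text supports it.

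**4. Does 45 count people screened or people who start?** Study consent follows the full work-up, and the possible delay is placed before enrolment. Both suggest that enrolment means joining the study after screening. They do not prove it.

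**5. Which denominator does the endpoint imply?** It counts patients retained as far as the injection. A patient who leaves during the taper was not retained and so is a failure; removing that patient from the denominator would contradict the word. Dividing by completers also fails on its own terms: if completers are the injected, the result is 30/30 = 100% whatever the treatment does.

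**6. How much could the choice of N matter?** With x injections, x/30 exceeds 65% when x > 19.5, so x ≥ 20. And x/45 is below 45% when x < 20.25, so x ≤ 20. Only x = 20 satisfies both:
- 20/30 = 66.7% (Clopper-Pearson 95% interval 47.2% to 82.7%)
- 20/45 = 44.4% (29.6% to 60.0%)

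The two intervals overlap widely. Unless 45 are enrolled and the analyst divides by an unplanned subset of 30, this compares two trials of different size, not two analyses of one trial.

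**The case for a change.** The strongest case is that several milestones precede the injection and the SAP does not rule any of them out as a denominator. Suppose 45 enrol, the true rate among all of them is 40%, and an analyst divides by the 30, 35 or 40 who reach some milestone (rate and counts all assumed). The chance of observing at least 45% is then 95%, 80% or 56%, against 22% on all 45. The arithmetic is right, but neither document proposes such an analysis, and it runs against the retention wording. It shows what a departure from the plan could do, not what the plan does.

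A second argument concerns the word completer. If it means finishing the study, 45 looks too few: 29.25 expected injections at 65%, and about 26, 23 or 20 finishers if 90%, 80% or 70% of injected patients stay (assumed). However, the SAP hypothesises at least 65%, so 29.25 belongs to the lower edge of that range, 0.75 of a patient short of 30. Later losses do not touch an endpoint settled at the first injection.

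A third argument is that recruitment might stop at 30 enrolled, at 45 enrolled or at 30 completers. The protocol does call 45 a projection. It is still the only enrolment figure given, so the intended size can be read.

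What stands is that completer is undefined, the SAP does not repeat the 45, and the primary analysis set is not named. Whether a patient who signs consent on Day 0 but takes no buprenorphine on Day 1 belongs in the denominator is also unsaid.

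**Conclusion.** No change to the plan is called for. The two documents do not contradict each other: the protocol relates 30 to 45, the SAP's 30 matches the completer figure, and 30/45 = 66.7% sits beside the 65% hypothesis. The endpoint wording leads an analyst to divide by everyone who starts and to count anyone without an injection as a failure. Naming that set would write down what a competent analyst would do anyway.

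The remaining choice, all who sign the study consent or all who take a first dose, differs only by patients lost between Day 0 and Day 1. The documents give no number for these, and either set is defensible. The study is small, single-arm and mainly descriptive, and its 30 is justified by safety, tolerability and working out the procedure, not by a test of 45% against 65%. No bias is shown.

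This conclusion assumes that patients in the endpoint means those who enter the study, and that the 45 are enrolled patients and not people screened. The text favours both readings without stating either. If the 45 included people who sign only the screening consent, the starting cohort would be smaller than 45, but the rule of counting the uninjected as failures would be the same.

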Select the names of persons designated to obtain consent/assent

[name], MD

Type in the name(s) not found in the above list

Study Procedures

Describe the procedures required for this study

Buprenorphine induction/stabilization/taper: Buprenorphine induction will be conducted at the SURC center. After consenting to the study, participants will receive buprenorphine, dispensed weekly, that they will take daily. Participants will be stabilized on, and tapered off, buprenorphine over a 3-week period. Reductions will occur in a graded fashion, with the stabilization dose reduced to 4mg, according to the following schedule:

- **Day 0 (Study Consent + ancillary medications).** Participants will be advised to abstain from opioids for at least 12-16 hours prior to taking their first dose of buprenorphine/naloxone in the clinic the next day.
- **Day 1:** After a COWS of 6-10, participants will receive buprenorphine/naloxone 2/0.5mg. If tolerated, the patient will receive an additional 4mg onsite, with 2mg to take home that evening. Patients will receive a total of 8/2mg on Day 1.
- **Days 2-7:** 8/2 mg buprenorphine/naloxone
- **Days 8-14:** 6/1.5 mg buprenorphine/naloxone
- **Days 15-21:** 4/1 mg buprenorphine/naloxone

Participants will attend the center twice weekly and will be assessed for opioid and other substance use (urine toxicology and self-report), vital signs, opioid withdrawal symptoms, opioid cravings, and dose adjustments of buprenorphine will be made as needed by study physicians. This approach to buprenorphine taper is intended to resemble standard clinical practice, in which patients seeking transition off buprenorphine undergo a slow taper. The purpose is in part to provide a slow transition with minimal withdrawal symptoms. Participants will have at least two study visits a week during the buprenorphine taper, but may be seen more regularly at the center if deemed clinically necessary. Participants will be required to submit at least one opioid negative urine (except for buprenorphine) during the last two weeks of the buprenorphine taper. **Participants who are not able to submit at least one opioid negative urine**

during the last two weeks of the buprenorphine taper will be offered buprenorphine to resume in the clinic and will be provided with referrals.

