Naltrexone induction procedure: Participants who successfully complete the taper must then complete a two-day washout (abstinence from opioids, buprenorphine). During this 48-hour period, participants will report to the center daily for vital sign monitoring and to receive standing doses of ancillary medications (clonidine, clonazepam, zolpidem, prochlorperazine) to alleviate withdrawal and discomfort with additional doses as needed. After abstinence of \geq 48 hours from the last buprenorphine dose, to allow for mu receptor availability, participants will begin the naltrexone induction, using a 3 day ascending taper of oral naltrexone and once the final oral dose of naltrexone 15 mg is tolerated, participants will receive Vivitrol injection.

The administration of naltrexone will occur within a detoxification suite, consisting of a private room outfitted with two comfortable reclining lounge chairs, adjustable lighting, and an entertainment system. Participants will be monitored by clinical staff frequently, with vital signs checks and withdrawal assessments. Transportation home by car service will be provided at the end of the day for any patient deemed to have this clinical need.

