On Day 1 of the naltrexone induction, participants are pre-treated with prochlorperazine, clonidine, and clonazepam, followed by the first dose of naltrexone 1.5mg. If the first dose of naltrexone is tolerated, a second dose of 1.5mg will be administered. Ascending split doses of naltrexone will be titrated up slowly, until the final total dose of 15mg has been given on Day 3 (Day 1: 1.5-3mg, Day 2 : 3-6mg, Day 3: 15mg). Ancillary medications will be offered daily during the induction week and will include clonidine for myalgias, prochlorperazine for nausea, clonazepam to reduce anxiety and dysphoria, and trazodone or zolpidem for insomnia. Participants will be provided take-home doses of ancillary medications in small doses for one week post-administration of Vivitrol. Once a total of 15mg of naltrexone has been tolerated (at least 1.5 hr. observation), the participant may receive 380mg IM Vivitrol. As noted in the section for Procedures for Missed Doses of Vivitrol, if relapse is suspected (the participant reports opioid use, and/or has a positive UDS for opioids) and there is a risk that the participant has developed physical dependence (e.g., delay in receiving scheduled injection or subjective effects suggesting that the block is incomplete) a naloxone challenge will be administered before the participant receives their next injection.

For female participants, a urine pregnancy test will be obtained on the day of Vivitrol administration. If at any time during the study a female participant has a positive urine pregnancy test, this will be reported to the FDA and IRB, the participant will be discontinued from the study, and transitioned to a treatment program in the community.

If a participant is unable to receive Vivitrol on induction Day 3, because they were unable to receive naltrexone due to opioid intoxication or severe withdrawal, the participant will be given up to two additional days to attempt the oral naltrexone titration and Vivitrol induction. **If a patient fails to succeed with the naltrexone initiation procedure, the study team will provide the patient with a weekly supply of buprenorphine, and will be provided with a referral.**

Vivitrol Injections: Vivitrol will be administered as an intramuscular injection (380mg) in one buttock by one of the research psychiatrists or research nurse, who are currently trained and administer Vivitrol in other

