protocols. Participants will be offered a second injection 4 weeks post administration of the first injection, and a 3rd injection 4 weeks later.

Procedures for Missed Doses of Vivitrol: If a patient misses a scheduled second or third injection and takes an opioid during at least two of the seven days following the date of the scheduled injection, relapse will be suspected (the participant reports recent opioid use, and/or has a positive UDS for opioids), a naloxone challenge may be performed, if appropriate, using 0.8mg naloxone IM. The patient is followed clinically and withdrawal symptoms are assessed over the next hour. If the challenge is negative, the administration of Vivitrol will be resumed. However, because there are blood levels and partial blockade beyond four weeks after the initial administration of Vivitrol, vulnerability to relapse may be more gradual, and the instance of mild or equivocal reactions to the naloxone challenge more common. In this instance, a second challenge within 72 hours, will be attempted, and if tolerated, the next injection of Vivitrol can be given. Patients who fail two consecutive naloxone challenges are considered to have relapsed and are referred for inpatient detoxification or agonist maintenance, as deemed clinically appropriate and in accordance with the patient's wishes. **Patients who fail two negative naloxone challenges will be given a week supply of buprenorphine and will be provided with referrals.**

Missing a scheduled Vivitrol injection is the most important threat to the success of Vivitrol maintenance. In the event of a patient missing a scheduled injection, staff will immediately attempt to contact the patient to re-establish commitment to the naltrexone treatment and reschedule the injection within a 24-48 hour period. If the patient cannot attend the treatment center within a two-day time-frame, or cannot be located, the treatment team will use previously obtained locator information in an effort to locate the patient through emergency contacts and try to get them in for a visit.

Study Visits

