Participants will be seen in the center twice weekly during the buprenorphine stabilization phase and daily on weekdays during the induction phase (Days 1-5). Once XR-NTX has been administered, participants will continue to be seen at the center twice weekly for 12 weeks. At each visit the patient will meet with the research assistant to complete research ratings. Research nurse collects safety measures and inquires about side effects. Side effects of study medications are reviewed weekly during the visit with a research psychiatrist, or more frequently if clinically indicated, and study psychiatrist will adjust medication dose if necessary.

At each visit the patient meets with the research assistant to complete research ratings, including self-report of withdrawal, mood, and drug use. The patient provides a urine sample under observation by a staff member at each visit. The sample is tested immediately for opiates with the iScreen system (Instant Technologies, Inc.). Vital signs are also taken. All data are then brought to the therapist and therapy session is held.

Participants may come to the center to be seen as frequently as needed. In particular, any participant who is experiencing protracted opioid withdrawal will be offered clinical contact on a frequent, even daily, basis. For clinical matters arising in the evenings or on weekends, participants will have access to the 24-hour emergency telephone service, staffed by physicians familiar with this protocol who can address patients' concerns.

Behavioral Therapy

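### Do the sleep and anxiety secondary outcomes lack a measure in a way that calls for a change to the plan?

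*SAP*

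**What the plan says.** The SAP (Secondary Endpoint) lists "Measures of opiate withdrawal and sleep (continuous, longitudinal" as outcome 2 and "Measures of mood and anxiety (continuous, longitudinal" as outcome 3. It gives no scale, item or score for either. The Analysis Plan adds only that most outcomes will be summarised descriptively.

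The protocol touches on measurement in several places:

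- **Consent Procedures (screening):** "The baseline evaluation includes a full battery of self-report measures". The battery is not itemised.
- **Study Procedures, buprenorphine phase:** at twice-weekly visits participants "will be assessed for opioid and other substance use (urine toxicology and self-report), vital signs, opioid withdrawal symptoms, opioid cravings".
- **Naltrexone induction procedure:** during washout "participants will report to the center daily for vital sign monitoring and to receive standing doses of ancillary medications". During naltrexone administration there are vital sign checks and withdrawal assessments.
- **Study Visits:** research ratings at each visit include self-report of withdrawal, mood and drug use.
- **Assessment Instruments:** 15 entries. HAM-D and SAFTEE are weekly. COWS and SOWS are daily in induction and bi-weekly otherwise.

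**The concern.** A continuous, longitudinal outcome needs a repeated reading on a defined scale. For withdrawal the reader can point to COWS and SOWS, and for mood to HAM-D. For sleep and anxiety no entry in the instrument list carries the name, and the visit descriptions mention neither as something rated. Elsewhere in the protocol they appear as targets of ancillary medication or as side effects.

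Two things would be at stake. If suitable items sit inside scales already in use, the choice of items and scoring could be made after the data are seen. If they do not, the readings would never be taken and could not be recovered at analysis.

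**Working it through.** No figure in the plan depends on this point, so the check is mainly a comparison of sections.

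**1. Explicit links in the SAP.** Outcomes 2 and 3 hold four constructs: withdrawal, sleep, mood and anxiety. The SAP ties an instrument to none of them (0 of 4). Withdrawal and mood look covered only because scale titles in the protocol happen to match. By title, 2 of 4 have a counterpart; by the SAP's own wording, all four are equally unlinked.

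**2. The instrument list.** Six of the 15 entries are confined to screening, baseline or end of study: MINI, psychiatric interview, medical history, physical exam, locator form and end-of-study form. The other 15 − 6 = 9 are repeated: urine toxicology, CGI-O, HAM-D, COWS, SOWS, SAFTEE, concomitant medications, craving scale and vital signs. None is titled for sleep or anxiety. HAM-D, SAFTEE, COWS and SOWS could contain relevant items, but the documents give no item content. The form asks for copies only where instruments are not standard, so item content would not be expected in the text.

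**3. Is the list complete?** Two comparisons suggest it is not.

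- Self-report of drug use is collected (Study Procedures, Study Visits) and feeds secondary outcome 5, yet no drug-use self-report form is listed.
- Study Visits has mood self-reported at each visit, that is, twice weekly or daily. The evident mood scale in the list, HAM-D, is weekly.

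The form prompt accepts a brief description. The screening battery is not itemised either, and nothing says that its measures are never repeated. Absence from the list is therefore weak evidence that nothing is collected.

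**4. Would the choice of scale change the data?** Yes, in density. Induction is "daily on weekdays during the induction phase (Days 1-5", with injection planned on Day 3, and if that fails "the participant will be given up to two additional days to attempt the oral naltrexone titration and Vivitrol induction". A weekly scale gives about 1 induction reading; a daily scale gives 3 to 5. Reading bi-weekly as twice weekly, with 12 post-injection weeks:

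- weekly scale: 3 + 1 + 12 = 16 readings
- COWS/SOWS schedule: (3 × 2) + 3 to 5 + (12 × 2) = 33 to 35 readings

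The end-of-study section puts the final day 28 days after the second injection, and "Participants will be offered a second injection 4 weeks post administration of the first injection". That makes 8 weeks: 3 + 1 + 8 = 12, or 6 + 3 to 5 + 16 = 25 to 27. The Compensation section implies $1,720 ÷ $40 = 43 paid visits, with no breakdown that reconciles it with these totals. The totals are therefore loose. On either schedule, though, repeated readings would be available.

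**5. What rests on sleep and anxiety?** The 65% hypothesis and the 45% floor both concern receipt of the first injection. The sample size of 30 is justified by safety, tolerability and protocol development. No test, threshold or decision uses a sleep or anxiety score.

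**The case for a change.** The strongest case for acting is that the remedy is cheap and the study has no comparator, so the description is the result. Unnamed items leave room for selective reporting. The SAP's Exploratory Objectives also ask whether the adjunctive medication doses are adequate. The protocol gives clonazepam for anxiety and trazodone or zolpidem for insomnia, so readings on anxiety and sleep bear on that question. If the forms in use hold no suitable item, the data will be missing for good.

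Some of this stands. Neither document names a measure for sleep or anxiety, and a report on these outcomes should say which scale or items were used. The rest goes further than the documents allow. Loss of data is a possibility, not something shown, because the list is demonstrably incomplete and the content of the scales is not given. Selective choice of items could colour a descriptive summary of a secondary outcome, but no conclusion about whether to pursue the procedure depends on it.

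**Conclusion.** No change to the plan is needed. The observation is literally right: no scale, item or score is named for sleep or anxiety, and 0 of the 15 listed instruments carries either name. It amounts to missing detail of a kind that analysts routinely settle from the case report forms when they summarise a descriptive secondary outcome. Adding a new rating would rest on the unshown premise that the present forms hold nothing usable, and deleting the two words would improve nothing.

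The effect on the primary endpoint, the benchmarks and the sample size is nil. At most, the sleep and anxiety parts of two secondary outcomes are affected. This conclusion assumes that the instrument list is the brief description its form prompt allows, and that the analysts will state which items they used. The documents cannot settle whether usable items exist; if none do, those two parts would go unreported and the rest of the study would be unaffected.
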